6.2 Study Duration and Study Schedule

Total duration of subject participation will be 5 years. Total duration of the study is expected to be 82 months. Duration of patient acquisition is hereby estimated to be 22 months. This estimate is based on the following assumptions:

- ACL-reconstruction surgeries performed monthly at the investigation site: 12
- Ratio of patients agreeing to participate: 60% (estimate based on internal data)
- Ratio of patients eligible for the study: 35% (estimate based on internal data)

The estimated patient allocation rate is therefore:

$$12/\text{month} * 0.6 * 0.35 = 2.52/\text{month}$$

Estimated duration for the acquisition of 56 patients is 22.2 months.

First-Patient-In: 07/2017

Last-Patient-Out: 04/2024

Statistics/Abstract: 12/2024

6.3 Methods of Minimizing Bias

6.3.1 Randomization

A two-staged randomization method will be used. To ensure adequate treatment distribution for interim analysis, the first block will contain 10 interventional and 10 control treatments. In the following, a block for the remaining treatment allocations will be used.

6.3.2 Blinding Procedures

The current clinical trial is designed as a patient-blinded study.

Group allocation cannot be blinded to the operator nor can the group allocation be blinded to the practitioner evaluating the radiological images at regular postsurgical follow-up visit and for safety assessment.

Concealment of group allocation to the patient is ensured. During surgery, graft preparation and graft insertion is outside the patient's field of view.

No radiological images will be shown to the patient as to not reveal group allocation.

6.3.3 Other Methods of Minimizing Bias

Patient subjective knee function will be assessed using German versions of validated questionnaires [69, 72]. KT-1000 arthrometer testing provides the means to objectively measure anterior knee stability [80].

6.4 Unblinding Procedures

At patient study end - planned or unplanned - the patient will be informed about his/her group allocation in the trial.

7 STUDY POPULATION

7.1 Eligibility criteria

7.1.1 General Criteria for Eligibility

Participants fulfilling all of the following criteria are eligible for the study:

- 18 to 60 years of age at entry.
- Males and females.
- An ACL insufficiency as determined by clinical examination (positive pivot shift and/or positive Lachman test).

The presence of any of the following criteria will render the patient not eligible for the study:

- Contraindications to the class of drugs under study, e.g. known hypersensitivity or allergy to the investigational product,
- Women who are pregnant or breast feeding,
- Medical condition or comorbidity that would interfere with study participation.
- Other clinically significant concomitant disease states (e.g., renal failure, hepatic dysfunction, cardiovascular disease, etc.),
- Acute or chronic infections (i.e. osteomyelitis) in the surgical site,
- Uncontrolled metabolic diseases, such as diabetes, osteomalacia, thyroid dysfunctions,
- Long-term cortisone therapy,
- Autoimmune diseases,
- Radiotherapy,
- Heavy smokers,
- Motion disorder,
- Known or suspected non-compliance, drug or alcohol abuse,
- Inability to follow the procedures of the study, e.g. due to language problems, psychological disorders, dementia, etc. of the participant,
- Participation in another study with investigational drug within the 30 days preceding and during the present study,
- Previous enrolment into the current study,
- Enrolment of the investigator, his/her family members, employees and other dependent persons.

7.1.2 Inclusion / Exclusion for Eligible Subjects

Eligible patients fulfilling all of the following inclusion criteria will be included into the study:

- Patient has reached skeletal maturity

- A complete ACL tear to be reconstructed using hamstring tendon autograft. The ACL injury can either be isolated or combined with one or several of the following injuries:
 - A meniscus tear that is either left untreated or treated with partial resection,
 - A small, stable meniscus tear treated with fixation, but fixation not interfering with the rehabilitation protocol,
 - Cartilage changes verified on MRI with arthroscopically determined intact surface or fissuring on the surface that do not reach subchondral bone or exceed 1.5 cm in diameter (Outerbridge grade I-III [81]).
- Harvested folded tendon (unsutured) has a diameter between 8 and 8.5mm at the end to be inserted into the femoral bone tunnel determined using a tendon thickness tester (Karl Storz).
- Tendon graft construct consists of one of the following:
 - Semitendinosus tendon quadrupled
 - Semitendinosus tendon quadrupled plus gracilis tendon doubled
 - Semitendinosus tendon doubled plus gracilis tendon doubled
- A normal joint status possibly combined with either one of the following findings:
 - A small-avulsed fragment located laterally, usually described as a Segond fracture,
 - Joint space narrowing grade 1 or osteophytes grade 1 as determined by the OARSI atlas [82].
- Informed Consent as documented by signature

Eligible patients fulfilling any of the following criteria will be excluded from the study:

- Prior fracture of the affected leg,
- Earlier major knee injury to the index knee,
- Associated posterior cruciate ligament injury or medial collateral ligament injury grade III in index knee,
- Previous or current ACL injury on contra-lateral leg,
- One of the following injuries to the index knee as visualized on MRI and/or arthroscopy:
 - An unstable longitudinal meniscus tear that requires repair and where the following treatment interferes with the standard rehabilitation protocol,
 - Bi-compartmental extensive meniscus resections,
 - A cartilage injury representing a full thickness loss with exposed subchondral bone (Outerbridge classification grade IV),
 - A total rupture of the lateral collateral ligament.
- Diameter of the tendon graft does not allow the use of the OCS (Irrespective of group allocation).
- Poor bone quality / missing bone material requiring alternative / additional graft-fixation.

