7.3 Assignment to Study Groups

A two-staged randomization scheme will be used. The first block will contain a total of 20 patients. The second block will contain a total of 36 patients. For each block, a container with sealed envelopes with paper cards for the group assignment (equally sized groups) will be prepared. At final inclusion of a patient, one sealed envelope will be drawn from the container and the patient will be assigned accordingly. After assignment, the paper cards are sealed again and stored in the patients case report file.

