8.3 Bone Tunnels

The harvested unsutured tendon-graft must measure between 8 and 8.5 mm in diameter at the end to be inserted into the femoral bone tunnel for subject inclusion (see chapter 7.1.2). Enlacing the OCS increases the graft diameter by 1 mm (Determined experimentally).

Accordingly, the overdrilled socket of the femoral bone tunnel has the following diameter depending on the subject's group assignment:

- Intervention group: 9 - 9.5 mm
- Control group: 8 – 8.5 mm

The tibial bone tunnel is drilled at a diameter of 8 ± 1 mm as applicable.

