9.3.2 Baseline (Visit 2)

9.3.2.1 Admission Interview

Eligible Patients giving oral consent to study participation will be interviewed by the SN for detailed screening of inclusion/exclusion criteria. A patient information eCRF will be filled covering all necessary points for temporary admission of the patient into the study. Definite admission can only be acquired after the surgery. The signed informed consent form will be validated by signature by the PI and stored in the patient's trial file. The patient will receive a copy of the signed informed consent form. For female patients of child bearing potential, a pregnancy test will be performed. The result of the pregnancy test will be photographed and the photograph will be signed by the PI and filed. The patient will be given the opportunity to clarify all uncertainties concerning the trial and the upcoming surgery with the PI. Also recorded will be the medical history and patient demographics. At this stage the preinjury activity level using Tegner activity scale will be assessed.

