9.3.2.3.2 Randomization

Patient randomization is acquired intraoperatively only if all inclusion criteria and no exclusion criteria have been met. The folded tendon-graft (not sutured, without OCS) must measure 8 – 8.5 mm in diameter at the end which is to be inserted into the femoral bone tunnel. If no intraoperatively assessed exclusion criteria are met (e.g. tendon-graft specifications, severe cartilage damage, extensive meniscus resection necessary) the subject is allocated to one of the two treatment groups. The envelope for the randomized group allocation of the subject is opened and the surgical procedure is carried out respectively. The envelope is sealed again afterwards and stored in the patient's trial file. The randomization procedure is described in detail in ACLROCS_WI_Randomization.

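### The plan does not fix when the bone-quality exclusion is judged, so a randomised patient can be removed under it by an operator who already knows the arm

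*Combined protocol and SAP*

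**What the plan says.** The last exclusion criterion in section 7.1.2 is "Poor bone quality / missing bone material requiring alternative / additional graft-fixation". It gives no time or method of assessment. The criterion just before it, on graft diameter, is explicitly neutral between arms: "Diameter of the tendon graft does not allow the use of the OCS (Irrespective of group allocation". The bone-quality criterion has no such qualifier.

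Two sections put eligibility before allocation. Section 7.3: "At final inclusion of a patient, one sealed envelope will be drawn from the container and the patient will be assigned accordingly". Section 9.3.2.3.2 (Randomization): "Patient randomization is acquired intraoperatively only if all inclusion criteria and no exclusion criteria have been met". The second gives examples of what is checked during surgery ("e.g. tendon-graft specifications, severe cartilage damage, extensive meniscus resection necessary") and then continues: "The envelope for the randomized group allocation of the subject is opened and the surgical procedure is carried out respectively".

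Section 9.3.2.1 (Admission Interview) places the decision later: "Definite admission can only be acquired after the surgery".

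Section 8.3 makes the femoral drilling depend on the allocation: "the overdrilled socket of the femoral bone tunnel has the following diameter depending on the subject's group assignment". The diameters are 9 to 9.5 mm for intervention and 8 to 8.5 mm for control.

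Four other provisions decide what happens to a patient who meets the criterion late:
- Section 7.4 withdraws a participant who meets an exclusion criterion in the course of the study.
- Sections 8.7 and 9.2.6 provide only for contact to obtain safety information once a patient has withdrawn.
- Section 11.4.1 names intention-to-treat but spells it out only for patients who do not follow rehabilitation.
- Sections 11.5 and 11.6 rule out imputation and replacement.

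Section 6.3.2 states that the operator cannot be blinded.

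**The concern.** An exclusion criterion protects a randomised comparison only if it is settled before anyone knows the allocation. This one is worded as a consequence of the operation, a need for other fixation, and fixation is the last part of the technique described in section 8.4. The final femoral socket must be drilled after the envelope is opened, because its diameter depends on the arm. A surgeon who meets weak or missing bone at that stage has a criterion that fits, a statement that admission is not yet definite, and a withdrawal rule that acts on it. The surgeon also knows the arm.

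At stake is the composition of the two groups at the 12-month CT. A patient removed this way has no assured CT, is not imputed or replaced, and is not clearly kept by the intention-to-treat definition. If bone quality is related to tunnel widening (plausible, but not stated in the documents), removals that differ between arms would bias the primary comparison.

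This is separate from the rule in section 8.8 on complications with the investigational product. That rule can act in the intervention arm only; the bone-quality criterion can act in both. Correcting section 8.8 would leave this route open.

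**Working it through.** **Step 1. Timing, passage by passage.**
- 7.3: the envelope is drawn at final inclusion, so inclusion comes before allocation.
- 9.3.2.3.2: no exclusion criterion may be met at randomisation; then the envelope is opened; then the assigned procedure is done.
- 8.3: socket diameter depends on the arm, so the final socket follows the envelope.
- 9.3.2.1: admission is definite only after surgery, hence after allocation.
- 7.4: a criterion met later leads to withdrawal.

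The first two and the fourth cannot all hold as written. Between the envelope and the end of surgery, a patient is randomised under 7.3 and 9.3.2.3.2 but not yet definitely admitted under 9.3.2.1. Section 7.4 supplies the rule that can remove the patient in that interval, and nothing in 11.4.1 overrides it.

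**Step 2. The plan's own figure, for scale.** Inputs from section 11.2: difference 20 points, SD 25.175, two-sided alpha 0.05, power 0.80.

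n per group = 2 × (1.96 + 0.842)² × 25.175² / 20² = 24.9, so 25. Total with 10% drop-out = 50 / 0.9 = 55.6, so 56, or 28 per group. The stated figures reproduce. (An exact t-test calculation gives 25.87, so 26 per group, and power 0.786 at 25; the difference is immaterial here.)

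**Step 3. How different the drilling is.** For the same graft the ratio of socket cross-sections is (9/8)² = 1.266 or (9.5/8.5)² = 1.249, so 25 to 27% larger with intervention. This shows that the bone removed differs by arm. It does not show that a need for other fixation differs.

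**Step 4. Size of a possible bias.** The documents give no rate for this exclusion, so every input here is assumed. If k of 28 intervention patients are removed and none in control, and those removed would have widened m points more than the rest, the intervention mean is flattered by (k/28) × m.
- k = 1, m = 25 (about one SD): 0.9 points.
- k = 3, m = 25: 2.7 points.
- Wider range: k = 1, m = 10 gives 0.4; k = 4, m = 50 gives 7.1.
- Equal removal of similar patients in both arms: near zero.

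The standard error of the difference with 28 per group is 25.175 × √(2/28) = 6.7 points. The 0.9 to 2.7 points are therefore 0.13 to 0.40 of a standard error.

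**Step 5. Loss of power.** With 10% drop-out and k further removals from the intervention arm only, t-test power is 0.789 for k = 0, 0.765 for k = 3 and 0.745 for k = 5.

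**The case against.** The strongest reply is that section 9.3.2.3.2 already settles the matter. Bone quality is an exclusion criterion, every exclusion criterion must be cleared before allocation, and the list of intraoperative checks is only a list of examples, so its silence on bone proves nothing. That section also refers to a separate work instruction on randomisation, which is not among the documents and may fix the timing. On this reading the sentence in 9.3.2.1 only reflects that graft and arthroscopic findings are still open at the interview; it states no rule for removing a randomised patient.

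Much of this stands. It does not close the gap, because 9.3.2.1 says after surgery rather than before allocation, and 7.4 removes a patient whose criterion comes to light later even if 9.3.2.3.2 was followed to the letter.

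A reader might go further and infer that the need for other fixation shows only after arm-specific drilling, so that eligibility depends on the arm and the larger socket costs the intervention arm more patients. The documents do not support that. No section says when poor or missing bone is recognised; imaging, arthroscopy or the 4.5 mm drilling common to both arms could reveal it first. Sections 8.1 and 8.4 describe the same femoral cortical fixation and the same tibial fixation in both arms, and section 3.1.1 says the scaffold has no primary fixation function. Nothing links the larger socket to a greater need for other fixation. Section 7.1 also excludes several conditions that could weaken bone, such as osteomalacia, long-term cortisone therapy and prior fracture of the leg, so such cases may be few.

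**Conclusion.** The concern holds in a limited form. The plan leaves the timing of the bone-quality exclusion open, contradicts itself on when admission is final, and contains a withdrawal rule that lets the criterion act after allocation, in the hands of an operator who knows the arm. The intention-to-treat definition does not clearly keep such patients.

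What is established is an open route to exclusion after randomisation, not a bias. The 0.9 to 2.7 points rest on three assumptions that the documents do not supply: how many patients are removed, that all are in the intervention arm, and that they would have widened about one SD more. Against a 20-point target the effect is modest, and it is near zero if the arms are affected alike. The point deserves correction because the correction is cheap and because outcome data not collected after a removal cannot be recovered at analysis.

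**What to change.** Reconcile sections 7.1.2, 7.3, 7.4, 9.3.2.1, 9.3.2.3.2 and 11.4.1 as follows.
- **7.1.2 and 9.3.2.3.2:** leave the clinical wording of the criterion, including its reference to fixation, unchanged. Add that it is judged, and the judgement recorded, before the allocation envelope is opened.
- **9.3.2.1:** state that admission is definite when the envelope is opened.
- **7.4 and 11.4.1:** state that a need for other fixation found after allocation is not a reason for withdrawal from the study. The patient is followed at all visits, including CT, and analysed in the assigned group.
- **9.2.4.3 and the eCRF:** add the fixation actually used, which the present list of surgical data does not include.

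These changes concern timing, follow-up and analysis only; the choice of fixation stays with the surgeon. The cost is a few sentences in an amendment and one eCRF field. The small downside is that a few patients with non-standard fixation stay in the data and add a little variance.

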7.2 Recruitment and Screening

Patients who will undergo ACL-reconstruction at Balgrist University Hospital will be recruited for this trial. All patients will be informed about the purpose of the trial, the operation modalities, and their benefits as well as risks. Patients will be asked whether they are prepared to participate in the trial prior to their inclusion. The patients will be handed out the written patient information brochure and will be given a minimum of 7 days for consideration. Patients that gave written informed consent will be screened for the inclusion and exclusion criteria of the current trial. Patients who were screened but not enrolled in the trial (including patients unable to give informed consent due to any reason) will be documented in the screening log, recording the reason for exclusion.

All travel expenses for study-visits outside of standard of care will be reimbursed in the following way:

- Public transportation ticket from domicile to study site and back (2. Class, no Halbtax), or

- In case of travel by car: 0.50 CHF per kilometer from domicile to study site and back.

Study-visits outside of standard of care and therefore object of reimbursement are: Visit 6 and 7.

7.3 Assignment to Study Groups

A two-staged randomization scheme will be used. The first block will contain a total of 20 patients. The second block will contain a total of 36 patients. For each block, a container with sealed envelopes with paper cards for the group assignment (equally sized groups) will be prepared. At final inclusion of a patient, one sealed envelope will be drawn from the container and the patient will be assigned accordingly. After assignment, the paper cards are sealed again and stored in the patients case report file.

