12.1.2 Specification of Source Documents

The following documents are considered source data, including but not limited to:

- SAE worksheets

- Nurse records, records of clinical coordinators, and
- Medical records from other department(s), or other hospital(s), or discharge letters and correspondence with other departments/hospitals, if participant visited any during the study period and the post study period.

Source data must be available at the site to document the existence of the study participants and substantiate the integrity of study data collected. Source data must include the original documents relating to the study, as well as the medical treatment and medical history of the participant.

The following information (at least but not limited to) should be included in the source documents:

- Demographic data (age, sex)
- Inclusion and Exclusion Criteria details
- Participation in study and signed and dated Informed Consent Forms
- Visit dates
- Medical history and physical examination details
- Key efficacy and safety data (as specified in the investigation plan)
- AEs and concomitant medication
- Results of relevant examinations
- Laboratory printouts
- Dispensing and return of study device details
- Reason for premature discontinuation
- Randomization number

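### Allocation is a free draw from a container of sealed envelopes during surgery, and the protocol describes no fixed order, numbering, custody, draw log or count that would reveal a discarded draw

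*Combined protocol and SAP*

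**What the plan says.** Section 6.3.1 sets two stages: a first block of 10 interventional and 10 control treatments, then one block for the remaining patients. Section 7.3 gives the block sizes as 20 and 36 and describes the device: "For each block, a container with sealed envelopes with paper cards for the group assignment (equally sized groups) will be prepared". The allocation itself reads: "At final inclusion of a patient, one sealed envelope will be drawn from the container and the patient will be assigned accordingly".

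On timing, section 9.3.2.3.2 states: "Patient randomization is acquired intraoperatively only if all inclusion criteria and no exclusion criteria have been met". Graft diameter, cartilage damage and the extent of meniscus resection are among the points judged during surgery before the envelope is opened.

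On what is kept, section 7.3 says "After assignment, the paper cards are sealed again and stored in the patients case report file", and section 9.3.2.3.2 says "The envelope is sealed again afterwards and stored in the patient's trial file".

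On blinding, section 6.3.2 says "Group allocation cannot be blinded to the operator".

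Three other places bear on the point. Section 9.3.2.3.2 refers to a work instruction, ACLROCS_WI_Randomization, for the detailed procedure. Section 12.1.2 lists a "Randomization number" among the items that source documents should contain. Section 9.3.2.1 treats admission before surgery as temporary and says that definite admission is obtained only after the operation.

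**The concern.** Where the operator must know the treatment, protection against selection at entry rests on two things: the next allocation is fixed before the patient is considered, and nobody can change it once it is seen. The described method gives neither. The draw is itself the randomizing act, so no order exists beforehand against which the draws could be checked. Re-sealing after use is routine, so an intact seal on a filed card says nothing about when or how often it was opened.

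The moment of the draw is also sensitive. It follows directly on intraoperative judgements about eligibility, and section 9.3.2.1 can be read as leaving admission open until after the allocation is known. If a draw could be repeated, or a patient's admission decided with the arm in view, the two groups might differ in graft, cartilage or meniscus status in ways that the comparison of tunnel volumes could not separate from the device effect.

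**Working it through.** **The plan's own figures.** Block 1 is 10 + 10 = 20 (6.3.1). Block 2 is 36 in equal groups (7.3), so 18 + 18. Together 20 + 36 = 56. This matches section 11.2: 25 per group gives 50, and 50/0.9 = 55.6, rounded up to 56. The counts are consistent, and the sample size does not depend on how the envelopes are handled.

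**What the protocol text provides, control by control.**

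| Control | What the text says |
|---|---|
| Order fixed in advance | Not described; any envelope in the container may be taken |
| Numbering | Not described for envelopes or cards; 12.1.2 expects a randomization number but no section says where it comes from |
| Who holds the container and who draws | Not stated |
| Date and time of each draw | Not described |
| Count of used and unused envelopes | Not prescribed; monitoring (12.3) names eCRFs and consents, whereas devices are to be reconciled and signed for (8.4.2, 8.11) |
| Fixed totals | Yes: 20 and 36 |
| Used card filed per patient | Yes, after re-sealing |
| Log of patients screened but not enrolled | Yes, with reason (7.2) |

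**What each kind of irregularity would leave behind.**

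- *Envelope lost or set aside.* The totals fall short of 20 or 36, so a count would show it.
- *Envelope opened, re-sealed and returned, and another drawn.* The container still holds the right number of cards of each arm. One card is filed for the patient, and it agrees with the treatment given and with the device accounts. No described record shows the first draw. The final arm sizes stay balanced; only which patient received which arm changes.

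**Size of one discarded draw.** Let p be the share of envelopes left for the preferred arm.

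Returned to the container: chance of the preferred arm = 1 − (1 − p)².

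- Start of block 1: p = 10/20 = 0.5, so 1 − 0.5² = 0.75.
- Start of block 2: p = 18/36 = 0.5, so again 0.75.
- Later in a block the figure moves with p: p = 0.4 gives 1 − 0.6² = 0.64; p = 0.6 gives 1 − 0.4² = 0.84.

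Set aside instead of returned, at the start of a block:

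- Block 1: 1 − (10/20)(9/19) = 1 − 90/380 = 0.763.
- Block 2: 1 − (18/36)(17/35) = 1 − 306/1260 = 0.757.

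With a single honest draw the chance is 0.50 in each case. The returned draw, which a count would miss, gives almost as much control as the set-aside draw, which a count would catch.

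**Order of eligibility and allocation.** Sections 7.3 and 9.3.2.3.2 put the draw at final inclusion, after all criteria have been checked. Section 9.3.2.1 puts definite admission after surgery, and hence after the envelope is opened. Read literally, both cannot hold.

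**The case against.** The strongest reply is that the detail sits in ACLROCS_WI_Randomization. Numbering, opacity, custody and a log may all be there, and the supplied documents cannot show otherwise. That stands as a limit on what can be claimed: the controls are not described in the protocol, which is different from saying that they do not exist. It does not dispose of the point. Section 7.3 describes a free draw. If the work instruction specifies a numbered sequence, the two disagree and 7.3 needs correcting; if it does not, the gap is real.

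A second reply is that drawing without replacement from a balanced set is a genuine chance mechanism, and that 9.3.2.3.2 already places the eligibility checks before allocation. Both are right. The weakness is that adherence to the method cannot be verified, not that the method fails to randomize.

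A reader might infer several stronger things, which the documents do not support:

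- *That the envelopes are unnumbered.* The text is silent, and the randomization number in 12.1.2 could be printed on the card.
- *That an envelope could be lost without trace.* Fixed totals, filed cards and the screening log mean that a count would show a shortfall, although no count is prescribed.
- *That people with a declared financial interest make the draw.* Section 2.6 declares ties to the funder but does not place those people in theatre, and no section says who draws.
- *That the predictability of the blocks measures the problem.* Someone who knows the block totals and counts past allocations can guess better than chance. That comes from the block sizes, and a numbered sequence with the same blocks would be equally predictable.

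**Conclusion.** The point holds as a gap in safeguards that should be closed. As described, an envelope opened, re-sealed and returned would not be revealed by any count or record that the protocol prescribes. One such event at the start of a block would raise the chance of a preferred arm from 50% to 75%. Sections 7.3, 9.3.2.1 and 9.3.2.3.2 also need to be reconciled on when eligibility becomes final.

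This rests on the protocol text alone, with the work instruction unseen. The 75% is conditional on one discarded draw for a given patient when the arms are equally represented in the container. It is not an estimate of how often this might happen, nor of bias in the treatment effect, and neither can be derived from the documents. Nothing in them suggests that any allocation was tampered with.

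**What to change.** Replace the container draw in 7.3 with a computer-generated sequence, keeping the blocks of 20 and 36. Someone outside the theatre team should prepare it before the first patient. Hold it in REDCap, which the trial already uses, or in sequentially numbered opaque envelopes. Release the next number only after intraoperative eligibility has been recorded and locked. Log the number, date and time of each release, and reconcile used numbers against the list at monitoring. The logged number then supplies the item that 12.1.2 asks for.

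Align 9.3.2.1, 9.3.2.3.2 and ACLROCS_WI_Randomization with the new text, so that one point in time is named at which eligibility is final and it precedes allocation. If the work instruction already contains these controls, bring them into 7.3.

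The cost is a protocol amendment submitted to the ethics committee (prior approval is needed if it counts as substantial, section 2.10), minor set-up including access from theatre if REDCap is chosen, and a list holder who is not in theatre. Block sizes, sample size and analysis do not change.
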